SkinStylus Microneedling System

Protocol for Clinical Study

Treatment of Ventral Torso Hypertrophic Scars

Trial Sponsor:

Esthetic Education LLC
[name]
[name]
[name]

Principle Investigator:

[name], MD

Trial number – 2017-002

04 August 2017

[figure not shown]
Protocol Synopsis for EE 2017-02

Title of Study:	The Clinical Efficacy And Safety Of SkinStylus Microneedling System for Ventral Torso Hypertrophic Scars: Clinical Results With 30 Patients
Principal Investigator:	[name], M.D. F.A.A.D
Study Design:	Blinded, bias minimized comparison of pre and post treatment photographs
Target Population:	General population over the age of 22
Duration of Study:	Approximately 6 months
Treatment	SkinStylus® Microneedling
Study Objective:	This is a study to evaluate the efficacy of SkinStylus Microneedling for ventral torso hypertrophic scars

PROTOCOL APPROVAL PAGE

We the undersigned have reviewed this protocol and agree that it contains all relevant information and appropriate safeguards for human participants as required by the UK MHRA, GCP, ICH and USFDA requirements.

[figure not shown]
We further agree that the protocol will be executed exactly as written and approved by the Institutional Review Board (IRB) and/or Ethics Committee. Any change required or proposed shall be reviewed by the IRB/Ethics Committee prior to its implementation.

[figure not shown]
[name]
Owner
Esthetics Education, Inc.

8/21/17

Date

PT

[name], MD

8/8/2017

Date

Investigator Signature Sheet

I have read the attached protocol and agree that it contains all the necessary details for performing the study.

I will provide copies of this protocol and of the preclinical information on the investigational product, which was furnished to me by the sponsor, to all members of the study team responsible to me who participate in the study. I will discuss this material with them to assure that they are fully informed regarding the study device and the conduct of the study.

Once this protocol has been approved by the Institutional Review Board (IRB), I will not modify it without obtaining the prior approval of the sponsor and of the IRB. I will submit the protocol modifications and/or any informed consent form modifications to the sponsor and the IRB, and approval will be obtained before any modifications are implemented.

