IV	21-27	Skin burns minimally, always tans well (moderate brown)
V	28-34	Skin very rarely burns, tans very easily (dark brown)
VI	35-36	Skin never burns, always tans (deeply pigmented dark brown to darkest brown)

5. Exclusion Criteria – patients with any of the following shall be excluded from the study.
 - a. Women who are or think they may be pregnant

- b. Participants currently taking Coumadin/Warfarin® or heparin
- c. Any type of bleeding disorder
- d. Any history of keloid formation
- e. Lidocaine, tetracaine, prilocaine, bupivacaine, or benzocaine hypersensitivity
- f. Patients with mental disorders
- g. Patients with metal implants around the proposed treatment areas
- h. Patients with any undefined wasting disease (Cachexia for example)
- i. Presence of an active infection in the treatment area other than mild acne
- j. Presence of tumors or those who are being treated by chemotherapy or radiation therapy
- k. Presence of severe cardiovascular and cerebrovascular disease
- l. Presence of renal failure

6. Withdrawal from the study - the patient will be withdrawn from the study upon his/her request or if the PI determines the patient has become part of the excluded population. For example, during the trial a female participant discovers she has unexpectedly become pregnant.

7. The PI or his designee will discuss the study with each potential participant reviewing the SkinStylus® and its operation, the treatment protocol, the need of completion of the trial as written, the inclusion and exclusion criteria; the warnings and contraindications and the taking of photographs prior to obtaining informed consent. Any potential participant not meeting all the selection requirements shall not be accepted into the trial and therefore no informed consent from them shall be required.

8. Adverse Incidents – adverse incidents are defined above. The PI shall be immediately informed whenever an adverse incident, as defined above, is detected or even suspected to have occurred. The circumstances relating to adverse incidents, their resolution and the participant's condition and treatment shall be recorded on the CRF.

9. Photographs

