- b. The technician administering the treatment shall further clean the treatment areas, if necessary.
- c. The hypertrophic scar to be treated shall be divided into two equal segments and the technician shall randomly choose one half to be treated.

- d. The technician shall describe in the CRF, which half of the scar was treated.
- e. Subsequent treatments shall only treat the same half of the scar that was initially designated the treatment side.
- f. If the scar is to be locally anesthetized, the entire scar (both halves) are to be anesthetized.
- g. A proprietary glide serum, EstheCeuticals® HA-Cu Serum, shall be applied prior to treatment and again as necessary. The purpose of the serum is to act as a glide and no therapeutic effect is known or anticipated. This serum has been used in several hundred microneedling treatments without any incidence of adverse events.
- h. The depth settings and clinical endpoints shall be established by the PI.
- i. Each participant shall receive three SkinStylus treatments .
- j. Each participant shall receive one treatment using each of the three different array configurations. The order in which each is used shall be randomized at intake but a different array configuration must be used in each of the three treatments.
- k. The treatments shall be not less than 12 days or more than 14 days apart.
- l. The treatments shall consist of 2 to 3 passes at the targeted area over a period of 15-30 minutes.
- m. While the technician may adjust the treatment settings, the treatment settings shall remain within the range specified by the PI, usually 2.5mm depth.
- n. At the conclusion of treatment the technician completes the CRF as stipulated.
- o. 90 days following the final treatment the post treatment photograph shall be taken and recorded in the CRF. There may be other photographs taken periodically during the trial in addition to the dermal spectroscope readings taken.
- p. 180 days following the initial treatment the patients shall be evaluated to provided objective evidence of what adverse incidents, as previously defined, may have occurred.

D. Determination of Results

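### Three needling sessions on the same scar half are fixed 12 to 14 days apart, with no provision to hold a session while an adverse incident is unresolved

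*Combined protocol and SAP*

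**What the plan says.** All references are to the combined protocol and SAP.

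- **Schedule (C.12, Sequence of Treatment).** C.12.i: "Each participant shall receive three SkinStylus treatments". C.12.j adds that "a different array configuration must be used in each of the three treatments", so a missed session also means a missed array. C.12.e: "Subsequent treatments shall only treat the same half of the scar that was initially designated the treatment side". C.12.k: "The treatments shall be not less than 12 days or more than 14 days apart".
- **Adherence (Protocol Approval Page).** The signatories agree that "the protocol will be executed exactly as written", with ethics review before any change.
- **Incidents (Safety Endpoint).** Six conditions count as adverse incidents: pruritus beyond 24 hours, pain beyond 2 hours, infection of the treated area, fever, pigment change that lasts 90 days, and petechiae beyond 1 hour.
- **Response (C.8).** "The PI shall be immediately informed whenever an adverse incident, as defined above, is detected or even suspected to have occurred". The CRF must also carry an account of each event, including how it resolved, how the participant fared and what care was given. The item says nothing about the next session.
- **Withdrawal (C.6 with C.5.i).** A participant leaves the study on request or "if the PI determines the patient has become part of the excluded population". Active infection in the treatment area, mild acne excepted, is on the exclusion list. None of the other five incidents is.
- **Late safety evaluation.** Safety endpoint analysis counts 180 days from the last treatment. C.12.p counts 180 days from the first.

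**The concern.** The schedule has a ceiling as well as a floor, and nothing in C.12 connects it to the incident rules in C.8. Suppose a participant still has an unresolved incident from the previous session, and the PI already knows of it. Needling the same tissue again on day 14 complies with the text, while waiting until day 16 does not. In a device study of an elective cosmetic treatment, the written rule should point the other way.

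The second issue is follow-up. C.6 withdraws an infected participant from the study as a whole. It does not say whether that person stays for the 90-day photograph or the 180-day evaluation. Patient Population replaces dropouts beyond five so that at least 30 complete, and Section E bases the analysis on 30 subjects with assessable data. Participants stopped because of a reaction could therefore be missing from the efficacy comparison, and from the safety endpoint, which is judged on how few incidents occur.

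**Working it through.** The plan states no figure on this point, so there is none to reproduce. The check is a day count and a matching of rules.

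**1. Schedule (C.12.i, C.12.k).** Take session 1 as day 0. Session 2 falls on day 12–14. Session 3 falls between 2 × 12 = day 24 and 2 × 14 = day 28.

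**2. When each incident can be established (Safety Endpoint), and what follows.**

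| Incident | Established | Before next session (day 12)? | Time left to resolve by day 12 | Rule on further treatment |
|---|---|---|---|---|
| Pruritus | 24 h | Yes | 12 − 1 = 11 days | None |
| Pain | 2 h | Yes | 12 − 2/24 = 11.9 days | None |
| Petechiae | 1 h | Yes | 12 − 1/24 = 12.0 days (rounded) | None |
| Fever | At onset | Yes | Onset not limited | None |
| Infection | At onset | Yes | Onset not limited | Withdrawal (C.5.i with C.6, PI's determination) |
| Pigment change | 90 days | No | – | None |

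Pigment change after session 1 cannot count before day 90, which is 90 − 28 = 62 to 90 − 24 = 66 days after session 3.

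**3. Counts.** Establishable before the next session: 6 − 1 = 5. Of these, with no rule on the next session: 5 − 1 = 4. With PI notice and CRF recording under C.8: 6 of 6.

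**4. What a hold would breach.** Deferral past day 14 departs from C.12.k. Omission departs from C.12.i and C.12.j.

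**5. The 180-day evaluation.** Under C.12.p it is day 180, that is 180 − 28 = 152 to 180 − 24 = 156 days after session 3. Under Safety endpoint analysis it is 24 + 180 = day 204 to 28 + 180 = day 208. The two differ by 24–28 days. Each day of deferral takes a day off post-treatment follow-up under C.12.p and none under the other rule.

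**6. How many participants (assumption, not an estimate).** Let r be the chance of reaching a later session with an incident unresolved. There are two such occasions, taken as independent, and 35 participants (the minimum in Patient Population). The chance per participant is 1 − (1 − r)².

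- r = 1%: 0.0199, or 0.7 of 35 expected; the chance of at least one is 1 − 0.99^70 = 0.505.
- r = 5%: 0.0975, or 3.4 of 35.
- r = 10%: 0.19, or 6.65 of 35.

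The lower end is the more plausible, given the time left to resolve in step 2.

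**The case against.** The strongest reply is that the plan already protects the participant. The 12-day floor is itself a recovery interval. The review quoted under Research Supporting Safety reports an intact epidermis at 24 hours and calls adverse effects uncommon and short-lived. The PI is a physician who must be told of any incident at once, sets depth and clinical endpoints (C.12.h), and has signed to work under GCP, the federal regulations and the Declaration of Helsinki as well as the protocol. The RN Monitor reports possible injury, and the participant may stop at any time. The instructions for use, the warnings named in C.7 and the CRF are not shown, and any of them may carry a retreatment caution.

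Much of this stands. It makes harm unlikely, and a PI bound by GCP would probably hold the session. It does not change the text. The floor is a fixed time, not a check on recovery. C.12.h gives no authority over the number or spacing of sessions. Monitoring visits are not tied to sessions. Fever can begin at any time in the interval, so the long resolution times for pruritus, pain and petechiae do not cover it.

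Two stronger readings are tempting, and the documents support neither. A reader might infer that only infection has any written consequence; C.8 gives all six incidents one, and what is missing is a consequence for further treatment. A reader might also infer that participants will in practice be re-needled over unresolved reactions. The documents give no frequency for that, and the PI's other duties point against it.

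**Conclusion.** The gap is real and moderate in weight. The plan requires three sessions on one half within a 14-day ceiling, with no recovery condition and no allowance to defer or omit. Four incidents that can be known before the next session (pruritus, pain, fever, petechiae) carry no instruction for it. The fifth, infection, leads to withdrawal only by reading two items together, on the PI's determination, and with no provision for follow-up.

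The number affected is unknown and probably small. The conclusion rests on reading C.12 literally, as the approval page invites, and on no retreatment rule existing in the documents not shown. Confidence is medium for that reason. The amendment is still worth making, because it makes the course a careful PI would take the compliant one and keeps those participants' data.

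Pigment change is left out of the pre-session check: the Safety Endpoint section treats it as expected if it resolves within 90 days, and both later sessions fall well inside that period.

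**What to change.** 1. **C.12.i–k.** Before sessions 2 and 3 the CRF records whether any listed incident is unresolved. If one is, the PI shall defer the session beyond day 14 until resolution is documented, or omit it. State that this is neither a withdrawal nor a protocol deviation. Keep the 12-day minimum.
2. **C.6.** Add wording such as: a participant whose treatment is stopped for an adverse incident, including active infection, stops treatment only. Unless they decline, they remain for the photograph 90 days after the last session given and for the 180-day safety evaluation. They are kept in the primary paired comparison, and the number and timing of sessions and the arrays received are reported.
3. **C.12.p.** Count the 180 days from the last session given, as Safety endpoint analysis does. The evaluation then moves with any deferral. If session 3 is omitted, for example, it falls on day 12 + 180 = 192 to 14 + 180 = 194.

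**Cost.** One CRF entry at two visits already planned, and amended wording in three places. C.9.a already has the number of treatments recorded with each photograph. The downside is that a few participants will have later or fewer sessions, or not all three arrays, which may slightly dilute the measured effect.
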